## **8.5.2. Safety Criteria for Suspending or Stopping a Cohort**

### **8.5.2.1. Dose Escalation Cohorts (First in Human)**

Any of the following criteria will be considered as stopping criteria for either stopping a cohort or stopping progression to the next higher dose level:

- The mean  $\text{AUC}_{0-\text{last}}$  from PK plasma results is greater than the max AUC reported in the 13-week topical ocular toxicity study in NHP (Study 57012928) [i.e., 8.04 (hr\*ng)/ml]
- $\geq 50\%$  of subjects within a cohort meet stopping criteria or are withdrawn by the PI (for other than personal or administrative reasons)
- $\geq 1$  Serious adverse event (SAE) which was considered treatment related and occurred while on study drug within 7 days of treatment
- $\geq 2$  AEs which were severe and considered treatment related and which occurred while on study drug within 7 days of treatment

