#### **6.4.2. Dose Escalation Cohorts**

##### *Cohort 1*

Once data at the Day 8 time point for the sentinel subjects are reviewed and judged satisfactory by the DEC, all remaining (3) subjects in this cohort can initiate dosing as described previously.

Following completion of all assessments on Day 8 (Visit 5A) for the entirety of cohort 1, the DEC will review safety and tolerability data. Once all applicable data through the Day 8 time point are reviewed and judged satisfactory by the DEC, a recommendation will be made to the Sponsor and documented regarding dose progression/escalation.

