##### *Cohorts 2 Onward*

Following DEC evaluation and approval of the safety of the previous dose level, the next higher dose level may initiate dosing for four subjects, who will be clinically evaluated at 48 hours, 72 hours and 7 days post-dose initiation (Day 8). Following completion of the 1-week clinical assessment comprising 7 days of continuous dosing, the DEC will review the safety and tolerability data. Once all applicable data at the 1-week point are reviewed and judged

satisfactory by the DEC, a recommendation to the Sponsor will be made and documented regarding dose progression.

Alternatively, safety data from the previous cohort may result in a DEC recommendation to repeat the previous dose level in the next sequential numbered cohort for an additional four subjects. These additional subjects will be clinically evaluated at 48 hours, 72 hours and 7 days post-dose initiation (Day 8). If the DEC judge the additional safety and tolerability data at that dose level to be satisfactory, a recommendation will be made and documented regarding dose progression and the next higher dose level can initiate dosing in the next sequential numbered cohort.

As there are three dose levels (low-, mid- and high-dose) with this adaptive design there can be as many as six dose escalation cohorts following the sentinel pair (should there be two cohorts at each dose level due to safety and tolerability findings at each DEC meeting).

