#### **8.4. Dose Adjustment Criteria and Dose Escalation Committee (DEC)**

The DEC will be established prior to Screening, the details of which will be set out in a DEC charter.

The DEC will provide recommendations about stopping, modifying or continuing the trial. The DEC will meet for cohort safety review to provide dose escalation recommendations.

Recommendations to escalate/maintain the dose will be made by the DEC in discussion with the PI, and based on a review of available clinical safety and safety laboratory data after completion of 7 days of treatment for each dose escalation cohort. An algorithm regarding progression to cohort expansion will be defined in a DEC charter. Details of the DEC's composition, roles and responsibilities will be described in the DEC charter. The Sponsor will chair the DEC. The DEC charter will include a definition of what safety observations would require a decision about dosing to be made.

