## 8.5. Stopping Criteria and Rescue Medication

The Investigator, the study MM (████████), the Sponsor MM or the DEC may decide to stop treatment for an individual subject for meeting the stopping criteria for individual subjects described in [Section 8.5.1](#). Subjects who do not meet individual subject stopping criteria at the clinical evaluation visits will continue dosing until the final day of dosing. Subjects who discontinue study drug will continue to receive safety and efficacy evaluation and all scheduled clinical assessments as well as follow-up.

Due to the naturally progressive nature of the disease, ophthalmic stopping criteria will specifically apply if any subject shows deterioration in their retinal health due to acceleration in the rate of disease, in the opinion of the Investigator. In such an occurrence, if a subject receives rescue medication, they will cease further dosing with study drug, and the last clinical observation will be carried forward for exploratory efficacy analyses. Assessments required for safety endpoints as well as exploratory efficacy will still be performed for any subjects receiving rescue medication, whereas the following assessments that are only required for efficacy endpoints will not:

- DRSS
- Automated Perimetry

The Sponsor MM and/or the DEC may recommend stopping dosing for a cohort or suspend progression to the next higher dose level due to meeting the stopping criteria for a cohort described in [Section 8.5.2](#).

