### 8.5.1. Safety Criteria for Stopping Doses for Individual Subjects

Subjects may withdraw at any time as detailed in [Section 15.1](#). Additionally, if at any time during the study the Investigator determines that a subject's safety is or has been compromised, the subject may be withdrawn from the study. Subjects may be discontinued from study drug prior to their completion of the study due to any of the following safety criteria being met.

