### **8.5.2.2. Dose Expansion (Using Highest Well-Tolerated Dose from Dose Escalation)**

Any of the following criteria will be considered as stopping criteria for stopping a dose expansion cohort:

- $\geq 50\%$  of subjects within a cohort meet stopping criteria or are withdrawn by the PI (for other than personal or administrative reasons)
- $\geq 1$  SAEs considered treatment related which were either severe, life-threatening or fatal
- $\geq 2$  AEs which were severe and considered treatment related and occurred while on study drug within 7 days of treatment

- $\geq 2$  SAEs considered treatment related which were either mild or moderate severity, not life-threatening and not fatal

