### **8.5.4. Pharmacokinetic Criteria for Adjustment or Stopping Doses**

Not applicable to this study.

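### The protocol's only exposure limit (section 8.5.2.1) is not reconciled with section 8.5.4 or with the data that section 8.4 gives the dose escalation committee

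*Combined protocol and SAP*

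**What the plan says.** Section 8.5.2.1 lists four criteria for stopping an escalation cohort or halting escalation. The first is a mean AUC0-last "from PK plasma results is greater than the max AUC reported in the 13-week topical ocular toxicity study in NHP (Study 57012928"; the figure given is 8.04 hr*ng/mL. Section 8.5 lets the Sponsor medical monitor and/or the dose escalation committee (DEC) recommend stopping a cohort or "suspend progression to the next higher dose level due to meeting the stopping criteria for a cohort". The Synopsis, under Stopping Criteria and Dose Holding, also ties holding and stopping to the cohort criteria, pending a decision by the investigator, the DEC and the medical monitors.

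Section 8.5.4 is headed for PK criteria on adjusting or stopping doses. Its whole content is "Not applicable to this study".

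On the data behind an escalation decision, section 8.4 says that recommendations are "based on a review of available clinical safety and safety laboratory data after completion of 7 days of treatment". The Synopsis (Analysis and Adaptive Design, and the DEC communication plan) and section 8.1 refer to safety and tolerability. Section 6.4.2 has the DEC review safety and tolerability, then continues for cohort 1 with "Once all applicable data through the Day 8 time point are reviewed and judged satisfactory by the DEC" and for later cohorts with "Once all applicable data at the 1-week point are reviewed and judged". None of these places names PK.

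The expansion list in section 8.5.2.2 opens with "Any of the following criteria will be considered as stopping criteria for stopping a dose expansion cohort" and contains no exposure criterion.

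**The concern.** One section sets a numerical PK stopping criterion. The section whose heading announces such criteria says that there are none to apply. The section that describes what the DEC looks at does not mention the data needed to check the criterion.

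This is a first-in-human study, and section 6.3 says that the human safety profile is not yet established. No other exposure limit appears: the expansion list has none, and the 2.3 nM Cmax in section 6.4.4 is a prediction. If the DEC follows section 8.4 literally, it can recommend the next dose level before anyone has compared the mean AUC with 8.04. Two readers could also disagree in good faith on whether the comparison is required at all.

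**Working it through.** **Can 8.04 be reproduced?** No. It comes from a monkey study report that is not among the documents. The dose multiples in section 6.4.4 do reproduce: 0.21/0.015 = 14, 0.21/0.030 = 7, 0.21/0.045 = 4.7 and 0.21/0.090 = 2.3. The main point is textual and does not depend on the figure.

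**The texts side by side**

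| Place | Is a PK stopping criterion in force? | Is PK among the DEC's data? |
|---|---|---|
| 8.5.2.1 | Yes, for escalation cohorts | Implied, since it cannot be applied otherwise |
| 8.5 and Synopsis (Stopping Criteria and Dose Holding) | Cohort criteria are acted on | Not stated |
| 6.4.1 | Going past the sentinel pair requires that no stopping criterion is met | Not stated |
| 8.5.4 | Not applicable, scope not limited | Not stated |
| 8.4 | Not stated | Clinical and laboratory safety data only |
| Synopsis (adaptive design, DEC plan) and 8.1 | Not stated | Safety and tolerability only |
| 6.4.2 | Not stated | Open: applicable data, not defined |

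The first column conflicts at 8.5.4 unless that section has a narrower scope than it states. The second column never answers the question.

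**Timing.** Escalation PK is drawn on Day 3 ± 1 (section 12.3.2) and the DEC reviews data through Day 8 (section 6.4.2). From draw to Day 8 is therefore 8 − 4 = 4 to 8 − 2 = 6 days. Section 13.3 gives no turnaround for PK results. Section 8.1 sets a minimum of 7 days between cohorts and no maximum. Waiting for results is thus permitted but not required.

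**Minor note: the AUC windows.** The Synopsis defines AUC0-t as running to the last measurable concentration, and the last draw is 4 h after a dose given twice daily. The human window is therefore known: it ends by about 4 h. The monkeys were dosed four times daily (sections 6.3 and 6.4.4), and no window is given for 8.04.

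- Molar mass from section 6.1: 72.92 ng/mL / 141 nM = 0.517 ng/mL per nM, or 517 g/mol.
- Predicted peak: 2.3 × 0.517 = 1.19 ng/mL. Held flat for 4 h, this bounds AUC0-4 at 4 × 1.19 = 4.76 hr*ng/mL.
- Average needed to reach 8.04 in 4 h: 8.04/4 = 2.01 ng/mL (3.9 nM), and 8.04/4.76 = 1.7 times the predicted bound.

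The half-life is not given. Assume one compartment, rapid absorption, near steady state, dosing every 12 h, and (also an assumption) that 8.04 is a 24-h monkey AUC. The share of a 12-h interval seen by 4 h is f = (1 − e^(−4k))/(1 − e^(−12k)), with k = ln 2/half-life. A human AUC0-4 of 8.04 then corresponds to a 24-h AUC of 2 × 8.04/f.

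| Assumed half-life (h) | f | 24-h AUC (hr*ng/mL) | Multiple of 8.04 |
|---|---|---|---|
| 1 | 0.938 | 17.1 | 2.13 |
| 2 | 0.762 | 21.1 | 2.62 |
| 4 | 0.571 | 28.1 | 3.50 |
| 8 | 0.453 | 35.5 | 4.41 |
| 12 | 0.413 | 39.0 | 4.85 |

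If 8.04 instead covers 4 h, the two AUCs are compared over equal time and the multiples do not arise.

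**The case against.** The strongest reply is that the sections can be read together. Section 8.5.1 is headed "Safety Criteria for Stopping Doses for Individual Subjects", whereas section 8.5.2 is about cohorts. Since 8.5.4 also speaks of doses, it may mean only that no PK rule governs an individual's dosing. Section 8.5.2.1 is specific and numerical, and the Synopsis and sections 8.5 and 6.4.1 all treat stopping criteria as operative. A mean AUC criterion cannot be applied without PK results, so PK is plausibly among the applicable data of section 6.4.2. The protocol leaves DEC details to a charter and assay methods to a Laboratory Manual, neither of which was available.

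Much of this stands. It makes it more likely that the limit is meant to apply, and it rules out any claim that the DEC will in practice decide without PK. It does not remove the conflict. Section 8.5.4 does not state the narrower scope, and the protocol does not keep such wording for individuals: the heading of section 8.4 uses dose adjustment for cohort-level decisions, and the Synopsis speaks of holding cohort doses. Section 8.4 still lists its data without PK.

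It is also fair that the other three criteria in section 8.5.2.1 work without PK, that section 6.3 anticipates very low systemic absorption, and that the lack of an exposure criterion in the expansion cohort is not an inconsistency.

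**Conclusion.** The point holds as a conflict within the protocol. One of the four escalation-cohort criteria, the only one based on exposure, is set in section 8.5.2.1 and left in doubt by section 8.5.4. The DEC's data as described in section 8.4 do not include what is needed to evaluate it. Escalation could therefore follow section 8.4 as written before the limit is checked. This rests on the protocol text alone; the DEC charter may already deal with PK.

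Three stronger inferences are not supported:

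- **The limit has been switched off.** The Synopsis and sections 6.4.1 and 8.5 point the other way.
- **The limit is too lenient because 4-h human exposure is set against longer monkey exposure.** The multiples of 2.13 to 4.85 need an assumed 24-h monkey AUC and assumed half-lives. No mismatch is shown; only the monkey window is missing. This part is minor and held with lower confidence.
- **A limit about 1.7 times the predicted 4-h bound is an error.** A stopping limit may properly lie above predicted exposure.

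**What to change.** - Reconcile sections 8.4, 8.5, 8.5.2.1 and 8.5.4 on whether the PK criterion is in force. If 8.5.4 is meant for individual doses only, say so there.
- Make sections 8.4 and 6.4.2 consistent with 8.5.2.1 by stating whether PK results are among the data the DEC has before each escalation decision, and align the DEC charter.
- As a minor addition, state the time window of the monkey AUC behind 8.04 next to the criterion.

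The cost is wording, with no new samples or visits. If PK results must be in hand before each decision, assay time could lengthen the gap between cohorts, for which the protocol sets no maximum. This review does not choose the limit, the window or the rule.

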#### **6.4.1. Initial Dosing Initiation and Continuation**

##### *Cohort 1 Sentinel Subjects (low-dose)*

The first two subjects in cohort 1 will be sentinel subjects (1 subject each randomized to EXN407 and vehicle) and will be dosed at least 1 week prior to the other three subjects of the cohort.

Immediately after dosing, and 48 hours and 72 hours post dosing (days 3 and 4) subjects in cohort 1 will be examined clinically for signs of intolerance of the study drug. If in the opinion of the Investigator the study drug has acceptable tolerability the subject will continue to be dosed through Day 7. Following the completion of all assessments on Day 8 (Visit 5A) for the low-dose cohort (cohort 1) sentinel subject pair, the DEC will review the experience of these subjects. If the safety and tolerability of study drug in both sentinel subjects is acceptable in the opinion of the DEC, and none of the stopping criteria are met, a recommendation to progress to the expansion cohort at a given dose level will be made to the Sponsor by the DEC, and all remaining subjects in cohort 1 may commence dosing.

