## 8.2. Number of Subjects

Up to approximately 48 subjects will be enrolled into this study.

- Three (3) subjects are expected to be randomized to low-dose, 2 subjects are expected to be randomized to placebo (cohort 1, N=5 total)
- Three (3) subjects to mid-dose, 1 subject to placebo (expected to be cohort 2, N=4 total)
- Three (3) subjects to high-dose, 1 subject to placebo (expected to be cohort 3, N=4 total).

The remaining subjects (up to 40 additional subjects) will potentially be assigned to additional cohorts of four subjects at a given dose level (three EXN407 subjects, one placebo subject), and the remainder will be assigned to the dose expansion cohort once the highest well-tolerated dose is identified. Decisions to escalate to the next higher dose level, to recruit an additional cohort at the same dose level, or to move to the dose expansion cohort, are dependent on emergent data and the outcome of near real-time safety review by the DEC. An algorithm regarding progression to cohort expansion will be defined in the DEC charter.

The sample size for this study is deemed to be sufficient to evaluate the safety and tolerability of EXN407 in this population and to gather efficacy data that will aid in powering future clinical trials.

The final number of subjects is dependent on whether any dose levels are expanded following evaluation of emergent data by the DEC but is not expected to exceed approximately 48 enrolled subjects in total.

As the main aim of this study is to generate information on the safety and tolerability of EXN407, subjects who are withdrawn from the study for reasons other than safety issues may be replaced at the discretion of the Sponsor and the Investigator.

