#### 8.5.1.1. Individual Subject Stopping Criteria

Any of the following criteria will be considered as stopping criteria for the study eye in individual subjects:

- An increase from baseline in CMT  $\geq 75 \mu\text{m}$  when seen across two consecutive visits
- A loss of  $\geq 15$ -letters of vision as determined by ETDRS, from the best previous in-study BCVA, due to DME, with current BCVA not better than baseline
- A loss of  $\geq 10$ -letters of vision from best previous in-study BCVA (determined by ETDRS), due to DME, seen across two consecutive visits, with current BCVA score not better than baseline
- Persistent intolerable ocular irritation or redness
- Development of persistent corneal opacities or severe keratitis

- An  $\geq 10\%$  increase in corneal thickness in the study eye based on pachymetry assessed at a consistent time of day
- Intraocular pressure (IOP) increase of 12 mmHg or more (from baseline measurements) confirmed upon repeat testing
- Occurrence of any severe graded AE that is assessed by the Investigator to be related to study drug
- Occurrence of any serious adverse event assessed by the Investigator to be related to study drug
- If a subject's CMT is 420  $\mu\text{m}$  or less, the subject is withdrawn from the study if there is BOTH a loss of BCVA of  $\geq 10$  letters AND an increase in CMT of  $\geq 50 \mu\text{m}$
- If a subject's CMT is  $>420 \mu\text{m}$ , the subject is withdrawn if there was also EITHER a loss of BCVA of  $\geq 10$  letters OR an increase in CMT of  $\geq 50 \mu\text{m}$
- The Investigator believes it is in the best interest of the subject to discontinue study drug dosing and/or initiate an anti-VEGF or other rescue therapy.

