### **12.3.5. Visit 6A – EOS / Day 36 ( $\pm 2$ Days)**

Subjects will return to the clinic for their EOS visit on Day 36 with a window of  $\pm 2$  days.

The following procedures will be conducted:

- Concomitant Medications
- AEs since the last visit
- Vital Sign Measurements - systolic and diastolic BP, heart rate, respiratory rate, body temperature
- Physical Exam (targeted physical exam only, see [Section 14.1.4](#))
- Weight measurement
- BCVA – to be done prior to all procedures requiring pupil dilation
- Blood draw for hematology, serum chemistry and coagulation
- Single 12-lead ECG
- Collection of urine for urinalysis
- All remaining Ophthalmic Exams/ Ophthalmoscopy
- SD-OCT
- CFP
- Tonometry to measure IOP
- Corneal pachymetry

This visit marks the end of participation in this study.

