## 14.2. Adverse and Serious Adverse Events

In this study, AEs will be reported for all subjects from the time of consent until the completion of the follow-up/EOS Visit. SAEs will be reported for all subjects (enrolled and not enrolled) from the time of consent. Adverse events reported from the time of consent to Day -1 will be recorded as pre-treatment AEs. TEAEs will be evaluated from the first administration of study drug until the follow-up/EOS Visit or up to a 30-day follow-up period for AEs deemed related to treatment. Adverse events that are ongoing at the EOS Visit will be marked as Not Recovered/Not resolved on the AE eCRF page (see [Section 14.3.4](#)).

All spontaneously volunteered and enquired for, as well as observed AEs, will be recorded in the subject's medical records and the eCRF.

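### Section 8.5.2.1: in a full escalation cohort, one related SAE with onset after the on-drug window but before EOS meets none of the four listed cohort stopping criteria; the window should be extended.

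*Combined protocol and SAP*

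**What the plan says.** Section 8.5.2.1 lists four criteria which, in its words, "will be considered as stopping criteria for either stopping a cohort or stopping progression to the next higher dose level". They are:

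- a mean plasma AUC above the highest value in the 13-week monkey study;
- at least 50% of a cohort meeting individual stopping criteria or withdrawn by the investigator;
- at least one "Serious adverse event (SAE) which was considered treatment related and occurred while on study drug within 7 days of treatment";
- at least two related severe AEs under the same on-drug, 7-day limit.

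On timing, section 6.4.1 has a sentinel subject who tolerates the drug dosed to the end of the week: "the subject will continue to be dosed through Day 7". Section 12.3.5 sets the last visit: "Subjects will return to the clinic for their EOS visit on Day 36", with a window of 2 days either side. Section 14.2 evaluates treatment-emergent events "until the follow-up/EOS Visit or up to a 30-day follow-up period for AEs deemed related to treatment".

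The neighbouring SAE criteria have no time limit. For individual subjects, section 8.5.1.1 has "Occurrence of any serious adverse event assessed by the Investigator to be related to study drug". For expansion, section 8.5.2.2 has at least one of "SAEs considered treatment related which were either severe, life-threatening or fatal", or at least two related SAEs of mild or moderate severity.

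Section 8.2 treats the choice "to recruit an additional cohort at the same dose level, or to move to the dose expansion cohort" as separate from the choice to escalate.

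**The concern.** The protocol treats one related SAE on drug as enough to put a cohort or the next dose level in question. The same event with onset two or three weeks later, judged related by the same investigator, is not listed. The first-in-human part, where least is known, therefore has a narrower SAE window than the expansion part. The protocol gives no reason for the difference.

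What is at stake is mainly progression, because subjects who started together have finished dosing by Day 8. The escalation decision rests on data through Day 8 (section 6.4.2), and cohorts need be only 7 days apart (section 8.1). A late event at one dose can therefore arise while the next dose is about to start or is already being given. After the high-dose cohort no planned higher level remains. The remaining decision is the move to expansion, which 8.5.2.1 does not name; there, up to 40 subjects are randomized to active drug or vehicle for 84 days.

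**Working it through.** No sample size or error rate bears on this point, so there is no plan figure to reproduce. The check takes one related SAE, after the window and before EOS, through each criterion.

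**Inputs.** Last dose Day 7 (6.4.1, 8.1). EOS Day 36 ± 2, that is Days 34 to 38 (12.3.5). Cohort sizes 5, 4 and 4, with 2, 1 and 1 on vehicle (8.2). Sentinel pair of 2 (6.4.1).

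**The four criteria.**

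1. AUC rule: based on exposure, not on events. Not met.
2. 50% rule: one subject is 1/5 = 20% or 1/4 = 25%. The rule needs 3/5 = 60% (2/5 = 40% falls short) or 2/4 = 50%. Not met. The exception arises while only the sentinel pair has been dosed: 1/2 = 50% if the denominator is dosed subjects, but 1/5 = 20% if it is the planned cohort.
3. SAE rule: outside the window. Not met.
4. Severe-AE rule: needs two events, under the same limit. Not met.

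A fatal outcome does not change this, since none of the four refers to death.

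**Length of the uncovered period.** On the strict reading, cover ends with dosing on Day 7. On the widest reading, 7 days are added after the last dose: 7 + 7 = Day 14.

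| Reading | EOS Day 34 | EOS Day 36 | EOS Day 38 |
|---|---|---|---|
| Cover to Day 7 | 34 − 7 = 27 days | 36 − 7 = 29 days | 38 − 7 = 31 days |
| Cover to Day 14 | 34 − 14 = 20 days | 36 − 14 = 22 days | 38 − 14 = 24 days |

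**Overlap with the next cohort.** Count days for the last-dosed subjects of one cohort and assume the earliest schedule: DEC clearance on Day 8 and the next cohort starting together on Day 9. Its seven dosing days are then Days 9 to 15 of the earlier cohort. All of them fall before Day 36, and on the strict reading all fall in the uncovered period. Recruitment and meeting time would make the real schedule slower.

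**End date for a reworded rule.** A fixed Day 36 does not fit everyone. A subject whose last dose is on Day 3, for example, has EOS at 3 + 28 = Day 31, and 30 days after last dose is 3 + 30 = Day 33. A subject who completes dosing reaches 30 days at 7 + 30 = Day 37, with EOS between Days 34 and 38. Taking the later of the two covers both cases.

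**The case against.** The strongest reply is that 8.5.2.1 is not the only route to a stop. SAEs are reported within 24 hours (14.4.1, 14.7). The DEC reviews safety data before each cohort and ad hoc (Synopsis, Initial Dosing and Dose Escalation; 6.4), and recommends on stopping or modifying the trial (8.4). Study termination for a changed risk/benefit is open to several parties (8.6). The charter is to define which safety observations call for a dosing decision, and also the algorithm for moving to expansion (8.4). Even a met criterion only allows doses to be held (Synopsis, Stopping Criteria and Dose Holding) or lets a body recommend stopping (8.5). All of this stands, and it limits the consequence. It does not bring the event under the listed criterion. The charter cannot be checked, and section 19.1 names the protocol and consent form for ethics approval, not the charter.

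A second reply is that the window fits a 7-day treatment and a Day 8 decision. That explains what the first decision can use. It does not explain why an event learned of later, while progression is still open or a higher dose is being given, should drop off the list.

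A third is that a longer window lets one mild or moderate late SAE count, whereas expansion requires two such events. That is true, but the present escalation criterion already has no severity test, and the change alters only its window.

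A reader might infer that escalation would carry on after a late related death, or that the trial has no rule for one. The documents do not support either: the discretionary routes are real and the charter is unseen.

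**Conclusion.** The point holds as a gap in the protocol's list. In a full escalation cohort, a single related SAE with onset after Day 7, or after about Day 14 on the widest reading, but before EOS meets none of the four criteria in 8.5.2.1. The uncovered period is 29 days (27 to 31 with the visit window) or 22 days (20 to 24). The sentinel pair on its own is an exception if the 50% rule is applied to dosed subjects. A second subject meeting individual criteria in a cohort of four would also trigger that rule, at 2/4.

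The day counts should not be read as a share of risk missed. The documents give no SAE rate, and section 6.3 expects systemic absorption and direct systemic effects to be very low. The conclusion assumes a literal reading of 8.5.2.1 and says nothing about the charter. It also makes no claim about the severe-AE criterion, which needs two events and carries the same limit in escalation and expansion. The change is worth making because the gap is clear and cheap to close.

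**What to change.** Reword the SAE criterion in 8.5.2.1 to: *at least one SAE considered treatment related, with onset from first dose through the subject's EOS visit or 30 days after the last dose, whichever is later*.

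State that, when met and pending DEC review, it applies to:

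- any escalation cohort then being dosed at the same or a higher dose;
- progression to the next dose level;
- the start of the expansion cohort.

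Mirror this in the DEC charter, including its algorithm for expansion. An end date is needed because section 14.7 has related SAEs reported at any time after the study; events beyond the window stay with Sponsor and DEC review under 8.6.

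The cost is one reworded criterion and a matching charter entry. No visits, subjects or planned waiting time are added, since AEs are already collected to EOS and section 14.2 already allows up to 30 days for related events. The downside is an occasional pause for a late SAE judged related, possibly in a masked vehicle subject: 2 + 1 + 1 = 4 of the 5 + 4 + 4 = 13 planned escalation subjects.
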